### 6.1.6. Sensitivity Analyses

To evaluate the robustness of the primary analysis results, the following sensitivity analyses of the primary efficacy endpoints will be performed, including different imputation methods for missing data:

#### 1. Sensitivity Analysis 1

Same as the primary analysis, a t-test will be performed for the Per-Protocol analysis set on observed case (OC).

#### 2. Sensitivity Analysis 2

#### 3. Sensitivity Analysis 3

A t-test using the last observation carried forward (LOCF) method described in Section 6.1.3 will be performed for the ITT analysis set.

#### 4. Sensitivity Analysis 4

[figure not shown]

[figure not shown]
#### 5. Sensitivity Analysis 5

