#### 9.6.4. Efficacy Analyses

##### 9.6.4.1. Primary Efficacy Analysis

The primary analyses of the mean IOP comparison between the control group and each of the two implanted groups at each time point from 1 week to 12 weeks will be based on [REDACTED]

[REDACTED] For each of the two implant groups, the least-squares mean of the treatment difference (Implant - Control) at each time point and the corresponding 95% confidence interval will be derived.

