**9.6.4.4. Subgroup Analysis**

For each sub-group described in Section 9.5.4.4, the repeated measurement model will be performed within each sub-group [REDACTED]

[REDACTED]

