## 1. Introduction

This Phase 2 study evaluates the safety and efficacy of two intraocular implants that elute travoprost at different rates in subjects with open-angle glaucoma (OAG) or ocular hypertension (OHT). The study duration is 36 months postoperative. One database lock will occur after all subjects have either completed the Month 36 visit or discontinued prematurely.

An analysis will be conducted after all subjects either completed the Month 3 visit or have discontinued prematurely prior to Month 3. At that time, the randomization code will be unmasked to the project team after all the data queries related to the efficacy and safety outcomes are resolved and corresponding data revisions are completed in the database.

This statistical analysis plan provides details of the planned analyses to be performed at the time of the Month 36 database lock. Shells of tables, listings and figures are presented in a separate document.

[figure not shown]
This document is based on Protocol Amendment 2 (16 September 2016). The statistical definitions and analytical methods described in this SAP supersede that in the protocol. Any revisions to the primary endpoint analyses and significant revisions to the secondary endpoint analyses will be made prior to the database lock. Reasons for such revisions will be described in the final Clinical Study Report (CSR).

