## 6. Efficacy Analyses

### 6.1. Primary Efficacy Endpoints Analysis

#### 6.1.1. Definition of Endpoints

The primary efficacy measure in this study is IOP. Diurnal IOP (measured at 8AM, 10AM, and 4PM) is evaluated at Baseline, Day 10, Week 6, and Month 3. Standard IOP (measured at 8AM) is evaluated at Week 4 and Months 6, 9, 12, 15, 18, 21, 24, 27, 30, 33, and 36. [REDACTED]

The primary efficacy endpoint is the diurnal IOP in the study eye at 8AM, 10AM, and 4PM at each of Day 10, Week 6, and Month 3 visits (9 timepoints).

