#### 6.1.2. Statistical Hypotheses

#### 6.1.3. Handing of Missing Data/Intercurrent Events for Efficacy Variables

The approaches listed below will be used for handling missing data/intercurrent events:

- **Observed Case (OC):** Missing data are not imputed. Only subjects with available data at the given time point are considered. OC will be the primary approach in the analysis of continuous efficacy variables.
- **Last Observation Carried Forward (LOCF):** The LOCF analyses will use the last observed non-missing, time consistent, evaluation for efficacy measures assessed to impute missing data at later visits. Baseline efficacy evaluations will not be carried forward. LOCF will be the secondary approach for sensitivity analysis of primary and secondary efficacy endpoints.

[REDACTED]

A high-contrast, black and white image showing a complex, abstract pattern of geometric shapes. The pattern consists of several large, solid black rectangles of varying widths and heights, arranged in a staggered, overlapping fashion. The background is white, and the edges of the rectangles are sharp, creating a digital or graphic design aesthetic. The overall composition is abstract and lacks any recognizable objects or text.

3

[REDACTED]

[figure not shown]

- **Non-Responder Imputation (NRI):** Subjects who have missing data or intercurrent events at the timepoint of interest are treated as though they did not respond to the treatment. NRI will be applied to the responder analyses.

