#### 6.1.5. Primary Analysis

A large rectangular area of the page has been completely redacted with black ink, obscuring several lines of text. The redaction is approximately 15 lines high and 10 lines wide.

The primary analysis will be performed for the ITT analysis set based on the observed case (OC), i.e., without missing data imputation.

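### The SAP's observed-case t-test gives a biased treatment difference when missingness depends on earlier IOP and the dropout pattern or IOP level differs between arms; a repeated-measures primary analysis avoids this at little cost

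*SAP*

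**What the plan says.** The SAP governs. Its Introduction states: "The statistical definitions and analytical methods described in this SAP supersede that in the protocol". In SAP 6.1.5 most of the text is blacked out. What can be read is: "The primary analysis will be performed for the ITT analysis set based on the observed case (OC), i.e., without missing data imputation". The test itself is legible only in SAP 6.1.6, under Sensitivity Analysis 1: "Same as the primary analysis, a t-test will be performed for the Per-Protocol analysis set on observed case (OC"). SAP 6.1.3 defines observed case: "Only subjects with available data at the given time point are considered". The other legible rule there for a continuous endpoint is last observation carried forward: "LOCF will be the secondary approach for sensitivity analysis of primary and secondary efficacy endpoints".

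The primary endpoint (SAP 6.1.1) is study-eye IOP at three clock times on Day 10, Week 6 and Month 3, so nine timepoints.

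The protocol reads differently. For each implant group, section 9.6.4.1 says "the least-squares mean of the treatment difference (Implant - Control) at each time point and the corresponding 95% confidence interval will be derived". The model name is redacted there, but section 9.6.4.4 on subgroups says "the repeated measurement model will be performed within each sub-group".

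**The concern.** A t-test takes one value per subject, so nine timepoints imply nine separate comparisons. A subject seen at Week 6 but not at Month 3 is left out of the Month 3 comparisons, and the Week 6 readings are not used. Calling the analysis set ITT does not change this. A likelihood-based repeated-measures model uses those earlier readings and is valid if missingness is explained by the observed data.

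Suppose subjects with high IOP are more often missing at Month 3, and this happens more in one arm. The observed mean in that arm is then too low and the treatment difference shifts. Differential dropout is plausible in this design, since implantation plus placebo drops is compared with a sham procedure plus timolol. What is at stake is the primary estimate and its confidence interval.

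**Working it through.** **Inputs from the documents.** About 150 subjects randomised 1:1:1, so about 50 per arm; two-sided 95% confidence level (SAP section 4). No SD, correlation or dropout rate can be read, so there is no figure of the plan's own to reproduce.

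**Assumed inputs.** SD 3.5 mmHg (range 3 to 4); between-visit correlation ρ = 0.4, 0.6 or 0.8; mean IOP 19 mmHg.

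**Scale.** The 95% CI half-width is 1.96 × SD × √(2/50). At SD 3.5 this is 1.96 × 3.5 × 0.2 = 1.37 mmHg. At SD 3 it is 1.18 and at SD 4 it is 1.57.

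**Why the arms must differ.** If missingness depends only on an earlier reading, the observed-case mean in one arm is off by −ρ × [p/(1−p)] × d. Here p is the proportion missing and d is how far the earlier IOP of those who go missing lies above the arm mean. If p, d and ρ are equal in both arms, the term cancels in the difference.

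Rough size: for a log-odds slope of 0.3 per mmHg, d is at most about 0.3 × 3.5² = 3.7. With ρ = 0.6 and p = 0.106 in one arm only, the bias is at most about 0.6 × (0.106/0.894) × 3.7 = 0.26 mmHg. The logistic curve flattens at high IOP, so the true value is lower.

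**Simulation.** Three visits, monotone dropout with logit = f + 0.3 × (last observed IOP − 19), 3,000 replicates per setting. Bias is in Implant − Control at Month 3, in mmHg, at SD 3.5, for ρ = 0.4 / 0.6 / 0.8:

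| Setting | Missing at Month 3 | Observed case | Repeated measures |
|---|---|---|---|
| Same rule, no true difference | 10% to 11% in both arms | −0.017 / −0.025 / +0.012 | −0.017 / −0.025 / +0.013 |
| Same rule, true difference −1 | 8% implant, 10% to 11% control | +0.021 / +0.054 / +0.072 | −0.006 / +0.006 / +0.004 |
| Control arm only, no true difference | 5% | +0.098 / +0.111 / +0.145 | +0.025 / +0.001 / −0.001 |
| Control arm only | 11% | +0.163 / +0.207 / +0.302 | +0.017 / −0.015 / +0.018 |
| Control arm only | 21% to 22% | +0.304 / +0.446 / +0.564 | +0.003 / +0.009 / −0.007 |

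Monte Carlo error is about 0.72/√3000 = 0.013, so the first row shows no bias. Over SD 3 to 4 the control-only ranges are 0.07 to 0.22 (5% to 6% missing), 0.11 to 0.41 (9% to 12%) and 0.20 to 0.76 (20% to 23%). With one rule in both arms and a true 1 mmHg difference, the range is 0.02 to 0.09.

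**Precision.** At SD 3.5 the two standard errors lay between 0.70 and 0.76 and never differed by more than 0.014.

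**Two further dropout models, SD 3.5.**
- Missingness in one arm rising with Week 6 IOP, with 3% missing at random in the other arm: observed-case bias 0.12 to 0.22 at 5% missing, 0.19 to 0.39 at 10% and 0.29 to 0.57 at 15%. The repeated-measures bias was under 0.02.
- Using all six earlier diurnal readings, with 5% to 16% IOP-dependent dropout in one arm only: observed-case bias 0.08 to 0.36. The likelihood estimate was under 0.02, with an equal or smaller standard error.

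Taken together, 5% to 16% missing at SD 3.5 gives 0.08 to 0.57 mmHg, or 0.08/1.37 = 6% to 0.57/1.37 = 42% of the CI half-width.

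**The case against.** A reader might infer that dependence of missingness on earlier IOP is enough to bias the result. It is not: with the same dropout rule and the same IOP distribution in both arms, the difference was unbiased. The larger figures need IOP-driven dropout in one arm and not the other, and the documents neither give a dropout rate nor say that poorly controlled subjects leave. They describe other routes: hypotensive medication may be added (SAP 2.2), and subjects who need further glaucoma surgery stay in follow-up (Protocol 10.7). Those subjects still have readings, which is an intercurrent-event question that this model does not settle by itself. The simulated dropout also depends on observed IOP, which suits the repeated-measures estimate by construction. All of this stands, and it limits the size of the point.

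A reader might also infer that the SAP contains no analysis valid under missing at random. The documents do not support that. The text of Sensitivity Analyses 2, 4 and 5 cannot be read, and the abbreviation list includes MMRM, MI, MAR and MNAR.

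Nor do they show that the method changed after the Month 3 unmasking, since the SAP's date is not available. They also do not show that Month 3 and Month 36 treat the same nine timepoints by different methods, since this SAP details only the Month 36 analyses.

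Finally, a nine-timepoint unstructured covariance has 9 × 10/2 = 45 parameters. The check with all six earlier readings showed no loss of precision, but convergence still needs a plan.

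**Conclusion.** The point holds in a limited form. The legible text makes the primary analysis an observed-case t-test. That the tests are run separately at each timepoint, and that the protocol's primary model was repeated-measures, are inferences from partly redacted text, though they are the natural reading.

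The observed-case difference is biased only if missingness depends on earlier IOP and the arms differ in dropout pattern or IOP level. Under the assumed inputs this is roughly 0.1 to 0.6 mmHg when 5% to 16% are missing in this way in one arm. It is under 0.1 mmHg when one rule applies to both arms and the true difference is 1 mmHg. Even the upper end is below one standard error (about 0.7 mmHg), and with few missing Month 3 readings the effect is small.

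It would be too strong to say that a formal test decision is at risk. SAP 2.2 specifies no formal efficacy hypothesis, so the effect is on estimates and confidence intervals, although the estimand in SAP 2.1 mentions non-inferiority. The change is worth making because it removes an avoidable bias at almost no cost.

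**What to change.** In SAP 6.1.5, make a repeated-measures model the primary analysis:

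- one model of all nine timepoints with treatment, timepoint and their interaction;
- unstructured covariance, with a pre-ordered fallback if it does not converge, for example Toeplitz and then compound symmetry;
- the least-squares mean difference and 95% CI for each implant versus timolol at each of the nine timepoints.

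Keep the observed-case t-test as a sensitivity analysis. If the t-test is to stay primary, the SAP should give the reason for departing from the protocol and name the repeated-measures model as the key sensitivity analysis, unless the unreadable text already does so.

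The cost is SAP wording and one model. MMRM and all three covariance structures are already in the SAP's abbreviation list. The small downside is that the convergence fallback must be stated in advance. Baseline adjustment and the handling of added IOP-lowering treatment are separate questions that this change does not settle.

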### 6.1.7. Summary of Planned Analyses

[figure not shown]

## 7. Safety Analyses

The safety analyses will be based on the safety analysis set.

### 7.1.1. Extent of Exposure

Duration of exposure to study treatment in days will be calculated using the study exit date – surgery date + 1. If the study exit date is missing for subjects with early termination, then the date of last visit will be used as the study exit date. Study duration will be summarized as continuous variable by treatment group for the Safety analysis set. A subject listing will be provided.

### 7.1.2. Adverse Events

All adverse event (AE) summaries will be restricted to Treatment Emergent Adverse Events (TEAE), which are defined as those AEs that occurred on/after the initial treatment at Visit 3. Verbatim terms reported by the study sites will be mapped to system organ classes (SOC) and preferred terms assigned using MedDRA (Medical Dictionary for Regulatory Activities) [REDACTED] for summary purposes. The adverse event listings will be displayed by treatment group. The number and of percentage subjects experiencing a particular event will be presented.

For a given AE and subject, if more than 1 severity grade is reported, the highest severity grade will be used for analysis.

If a subject experienced more than 1 relationship within an AE, the subject is counted once under maximum relationship. AEs with a missing relationship will be considered related for this summary; events classified as ‘possibly’, ‘probably’ or ‘definitely’ from eCRF will be considered ‘related’.

Adverse events will be classified into ocular AEs and non-ocular/non-study eye AEs. An ocular AE will be determined as indicated on the AE form of eCRF for the study eye only; a non-ocular/non-study eye AEs will include AEs with primary SOCs of eyes for non-study eye and AEs with primary SOCs not for eye.

All TEAEs, ocular TEAEs and non-ocular/non-study eye TEAEs will be summarized by treatment group separately in the following tables:

- Summary of adverse events
- TEAE by SOC and preferred term
- TEAE by SOC, preferred term and maximum severity.
- TEAE by SOC, preferred term and relationship (Related/Not Related) to study treatment.
- Serious TEAEs by SOC and preferred term.
- Ocular TEAEs by preferred term.

The TEAE listings will be prepared, sorted chronologically within subjects for the following types of AEs. Each listing will be displayed by treatment group.

- All AEs
- Serious AEs
- TEAEs leading to death
- TEAEs leading to withdrawal [REDACTED]

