**4. STUDY DESIGN**

**4.1. Description of Study Design**

This is a prospective, randomized, double-masked, active-controlled, parallel-group, multicenter trial comparing the efficacy and safety of the Model G2TR-[REDACTED] Travoprost Intraocular Implant and the Model G2TR-[REDACTED] Travoprost Intraocular Implant to topical timolol in subjects with OAG or OHT. Approximately 150 subjects will be randomized in the study. Subjects will be followed through 3 years. Throughout the entire study, both the study staff performing certain measures (see Section 7.3) and the subject will remain masked as to the identity of the study medication. There are two phases to the study - a screening phase and a 3-year treatment/follow-up phase.

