**9.6.5.3. Adverse Events**

All adverse event (AE) summaries will be restricted to Treatment Emergent Adverse Events (TEAE), which are defined as those AEs that occurred after the initial treatment at Visit 3. [REDACTED]

[REDACTED]. It should be noted that AEs that occurred after during the baseline washout will be summarized separated. The adverse event listings will be displayed by treatment group. The number of subjects experiencing a particular event, the percentage of subjects experiencing the event, and the total number of events will be presented. The following summaries will be created:

- TEAE by SOC and preferred term
- TEAE by SOC, preferred term and maximum severity. At each level of subject summarization, a subject is classified according to the highest severity if the subject reported one or more events. AEs with missing severity will be considered severe for this summary.
- TEAE by SOC, preferred term and closest relationship to study treatment (Related/Not Related). [REDACTED]
- Serious TEAEs by SOC and preferred term.

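### SAP 7.1.2 omits the total number of events that protocol 9.6.5.3 requires, so repeat adverse event episodes are missing from the arm-level summaries to which the SAP commits

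*SAP*

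**What the plan says.** Protocol 9.6.5.3 (Adverse Events) states: "The number of subjects experiencing a particular event, the percentage of subjects experiencing the event, and the total number of events will be presented". It then names the treatment-emergent adverse event (TEAE) tables to be produced.

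SAP 7.1.2 (Adverse Events) has the corresponding sentence: "The number and of percentage subjects experiencing a particular event will be presented". It lists six tables: an overall summary; TEAEs by system organ class (SOC) and preferred term; the same by maximum severity; the same by relationship; serious TEAEs by SOC and preferred term; and ocular TEAEs by preferred term. None is described as carrying an event count or an event rate.

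Two SAP rules reduce multiple reports further. For severity, "if more than 1 severity grade is reported, the highest severity grade will be used for analysis". For relationship, "the subject is counted once under maximum relationship".

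On precedence, SAP Section 1 says: "The statistical definitions and analytical methods described in this SAP supersede that in the protocol". The same section places the table shells in a separate document, which is not part of the public text.

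**The concern.** Protocol 9.6.5 plans no formal testing of safety, so the descriptive tables carry the arm-level safety comparison. Safety is also part of the study objective (protocol Section 2). Removing one of the three planned statistics from the adverse event summaries therefore takes away something a reader would have used.

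Follow-up is long: "The study duration is 36 months postoperative". Over that time a subject may report the same term several times, and the number and percentage of subjects do not change when that happens. With the subject total and the event total together, a reader can work out the average number of episodes per affected subject. With the subject total alone, that is not possible.

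**Working it through.** **1. The two sentences side by side**

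| Statistic per event | Protocol 9.6.5.3 | SAP 7.1.2 |
|---|---|---|
| Number of subjects | yes | yes |
| Percentage of subjects | yes | yes |
| Total number of events | yes: "and the total number of events will be presented" | not mentioned |

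**2. Could redaction explain the gap?** No. The SAP sentence is complete. The visible gaps in 7.1.2 fall at the MedDRA reference and at the end of the last listing item.

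**3. Which text governs?** SAP Section 1 gives the SAP precedence, and the SAP is based on this same protocol of 16 September 2016. The shorter list therefore applies to the Month 36 analysis.

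**4. Can the total be derived?** Yes. Protocol Section 10 requires a separate form for each adverse event, so the counts are already in the database.

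**5. How much can the subject count hide?** The plan states no figure to reproduce. The following is an illustration on assumed rates.

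- Arm size: the protocol (4.1) states "Approximately 150 subjects will be randomized in the study", allocated 1:1:1, so 150 / 3 = 50 per arm.
- Subject-years per arm if everyone completes: 50 × 3 = 150.
- Events = affected subjects × episodes per affected subject.
- Rate per 100 subject-years = 100 × events / 150.

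| Affected (assumed) | SAP table shows | Events at 1, 2, 3, 5 episodes each | Per 100 subject-years |
|---|---|---|---|
| 5 of 50 | 5 (10%) | 5, 10, 15, 25 | 3.3, 6.7, 10.0, 16.7 |
| 10 of 50 | 10 (20%) | 10, 20, 30, 50 | 6.7, 13.3, 20.0, 33.3 |
| 20 of 50 | 20 (40%) | 20, 40, 60, 100 | 13.3, 26.7, 40.0, 66.7 |

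**6. The same check with a count model.** Let event counts per subject be negative binomial with dispersion k, and fix the probability p of at least one event. Then 1 − (k / (k + m))^k = p, so the mean is m = k × [(1 − p)^(−1/k) − 1]. The Poisson limit is m = −ln(1 − p). Expected events per arm are 50 × m.

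| p | Poisson | k = 1 | k = 0.5 | k = 0.25 |
|---|---|---|---|---|
| 20% | 11.2 | 12.5 | 14.1 | 18.0 |
| 40% | 25.5 | 33.3 | 44.4 | 84.0 |

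For example, at p = 40% and k = 1, m = 0.4 / 0.6 = 0.667 and 50 × 0.667 = 33.3. At 40% incidence the range is 84.0 / 25.5 = about 3.3-fold; at 20% it is 18.0 / 11.2 = about 1.6-fold. The amount hidden is small when events are uncommon and scattered. It grows when they are common and clustered in a few subjects.

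**The case against.** Most of the case on the other side stands and limits the point.

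- **The data are not lost.** SAP 7.1.2 plans listings of all adverse events by treatment group, in time order within subject. With about 50 subjects per arm, repeat episodes can be read from them. A listing is still not an arm-level summary, and the protocol planned a summary.
- **Continuing ocular effects are reported elsewhere.** SAP 7.1.4 to 7.1.6, 7.1.10 and 7.1.11 summarise slit-lamp, gonioscopy, ophthalmoscopy, endothelial cell density and hyperemia results by visit and arm. They cover specified findings at scheduled visits, so they overlap with adverse event totals without replacing them.
- **The shells might contain a count.** They are not public, and the content of the overall summary table is not spelled out. The SAP text nevertheless names only subject statistics.
- **The SAP may lawfully simplify the protocol.** It may, but the visible text gives no reason for doing so here.

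A reader might go further and infer that the event total would separate a one-time surgical reaction from a continuing effect of the implant. It would not. Protocol Section 10 records one form per event with its duration, and 10.7 follows each event to its outcome. One uninterrupted two-year event therefore counts as one, just as a one-week event does.

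A reader might also infer that follow-up time goes unreported. SAP 7.1.1 summarises duration by arm and 5.1 summarises exit status by arm. What is missing is a time denominator in the adverse event tables, and the protocol never planned one.

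**Conclusion.** The gap is real, and its scope is narrow. A safety statistic that the protocol requires is absent from the governing adverse event summaries, with no visible explanation. What is lost is the arm-level view of repeat, separately reported episodes.

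The consequence is for reporting only: no test, alpha or power changes. The illustrated differences (up to 5-fold at one versus five episodes per affected subject, and about 3.3-fold in the count model at 40% incidence) rest on assumed rates, equal arms of 50 and, for the rates per 100 subject-years, complete 36-month follow-up. They show what subject incidence can conceal. The documents do not support reading them as a prediction that the arms will differ in this way.

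The one-count-per-subject rule is written out only for the relationship table. For the SOC and preferred-term tables it follows from reporting numbers and percentages of subjects. The conclusion also assumes that the unseen shells do not already include the total.

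**What to change.** In SAP 7.1.2, restore the total number of events beside the number and percentage of subjects in four tables:

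- the overall summary of adverse events;
- TEAEs by SOC and preferred term;
- serious TEAEs by SOC and preferred term;
- ocular TEAEs by preferred term.

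Leave the maximum-severity and relationship tables at one count per subject, because they classify each subject once by design. If the sponsor prefers to drop the total, the SAP should state the departure from protocol 9.6.5.3 and give the reason.

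Events per 100 subject-years by arm, using the duration already derived in SAP 7.1.1, is an optional addition.

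The cost is one sentence and one extra column in four tables, with no new data. Event counts also depend on how sites split an illness into episodes, so they should be read alongside subject incidence and not in place of it.

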**Treatment Phase**

Subjects will begin treatment following Visit 2. The visits scheduled during the treatment phase are: Visit 3 (Operative), Visit 4 (Day 1-2, 1-2 days), Visit 5 (Week 1-2, 10 days  $\pm$  3), Visit 6 (Week 4, 28 days  $\pm$  3), Visit 7 (Week 6, 42 days  $\pm$  3), Visit 8 (Week 12, 91 days  $\pm$  7), Visit 9 (Month 6, 182 days  $\pm$  14), Visit 10 (Month 9, 274 days  $\pm$  14), Visit 11 (Month 12, 365 days  $\pm$  14), Visit 12 (Month 15, 455 days  $\pm$  30), Visit 13 (Month 18, 547 days  $\pm$  30), Visit 14 (Month 21, 637 days  $\pm$  30), Visit 15 (Month 24, 730 days  $\pm$  60), Visit 16 (Month 27, 820 days  $\pm$  60), Visit 17 (Month 30, 910 days  $\pm$  60), Visit 18 (Month 33, 1000 days  $\pm$  60) and Visit 19 (Month 36, 1095 days  $\pm$  60).

There are three treatment groups in the study and 1:1:1 randomization. Subjects will be randomized at the operative exam to receive treatment with either a high elution rate implant with placebo eyedrops instilled twice daily, a low elution rate implant with placebo eyedrops instilled twice daily, or a sham surgical procedure and twice-daily timolol. The operative exam will consist of surgery to implant one of the two implant designs in subjects randomized to one of the travoprost-eluting implant groups, or a sham surgical procedure in subjects randomized to the timolol group.

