**9.6.5. Safety Analyses**  
No formal statistical testing will be conducted for the safety analyses. No imputation will be performed for the missing values. All summaries will be based on the available data of the safety population. The descriptive statistics described in Section 9.6.1 will be performed at each visit for the 3 treatment groups separately. Sections below described specific data handling for study drug exposure, surgical complications, adverse events, and best spectacle corrected visual acuity (BCVA).

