## 2.2. Study Design

This is a prospective, randomized, double-masked (IOP observer and subject), active-controlled, parallel-group, multicenter trial. A total of approximately 150 males and females  $\geq 18$  years of age who were diagnosed with either Open-angle glaucoma (OAG) or Ocular hypertension (OHT) will be randomized to one of three treatment arms in a 1:1:1 allocation:

- [REDACTED]: Travoprost Intraocular Implant, model [REDACTED] (high elution rate) with masked postoperative one drop twice daily (BID) artificial tears in the study eye.
- [REDACTED] Travoprost Intraocular Implant, model [REDACTED] (low elution rate) with masked postoperative one drop BID artificial tears in the study eye.
- Control: Sham surgery with masked postoperative one drop BID topical timolol maleate, ophthalmic solution, 0.5% in the study eye.

Subjects are required to meet all eligibility criteria at the Screening visit. If the subject is using ocular hypotensive medications at this visit, she/he is required to complete the appropriate medication washout period before returning for the Baseline visit. [REDACTED]

Following completion of the baseline visit, eligible subjects are scheduled for the operative examination. At this visit, subjects will be randomized to treatment and per randomized assignment, either implanted with [REDACTED], or have the sham surgical procedure performed.

[figure not shown]
Follow-up visits are scheduled at postoperative Day 1-2, Day 10, Weeks 4, 6, Month 3 and every 3 months thereafter through Month 36. [REDACTED]

Postoperatively, for the duration of the study, subjects in the [REDACTED] arms are instructed to use topical eye drops (artificial tears) twice daily in the study eye, while subjects in the control arm, following sham surgery, are instructed to instill topical timolol 0.5% eye drops, solution twice daily in the study eye. The investigator could administer or prescribe ocular hypotensive medication [REDACTED] at [REDACTED] or later after the operative exam. [REDACTED]  
[REDACTED]

The pre-specified primary efficacy endpoint is IOP at each of the nine time points through 3 months postoperative (8:00 am, 10:00 am, and 4:00 pm at Day 10, Week 6, and Month 3). No formal statistical hypotheses for the efficacy endpoint were specified.

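### SAP 7.1.2 defines its two adverse-event classes on different bases, so an event can fall in both or in neither

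*SAP*

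**What the plan says.** SAP section 7.1.2 announces a two-way split: "Adverse events will be classified into ocular AEs and non-ocular/non-study eye AEs". It then gives each class its own rule.

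- Ocular: "An ocular AE will be determined as indicated on the AE form of eCRF for the study eye only". SOC plays no part in this rule.
- The other class: "a non-ocular/non-study eye AEs will include AEs with primary SOCs of eyes for non-study eye and AEs with primary SOCs not for eye". The second half of this rule looks only at SOC. It has no condition on the eye and does not exclude events already classed as ocular.

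The SOC comes from a separate step, the MedDRA coding of the site's verbatim term. Three sets of tables follow: "All TEAEs, ocular TEAEs and non-ocular/non-study eye TEAEs will be summarized by treatment group separately in the following tables".

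Protocol section 9.6.5.3 lists its own summaries, beginning with "TEAE by SOC and preferred term". Its readable text has no ocular/non-ocular split. SAP section 1 states that the SAP's definitions take precedence over those of the protocol, so the wording in 7.1.2 governs.

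**The concern.** A split works only if every event lands in exactly one class. Here one class is set by a mark on a form and the other partly by a coding result, and nothing in the readable text makes the two rules complements or says which prevails. Two faults follow. Some events can meet both definitions, and some can meet neither.

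The treatments are an intraocular implant or a sham procedure in one eye, so the split is how a reader separates local events from the rest. An event in both classes would also appear in a table whose title says that it does not concern the study eye. An event in neither class would be missing from both split sets and visible only in the tables of all TEAEs and in the listings.

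**Working it through.** **Inputs.** The two class rules are those of SAP 7.1.2. The plan states no figure to reproduce, so the check is to apply both rules literally to every combination of form mark, primary SOC and location. A sound split gives 1 in the last column of every row.

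| Row | Marked ocular for study eye on eCRF | Primary SOC | Location | Ocular | Non-ocular/non-study eye | Classes |
|---|---|---|---|---|---|---|
| 1 | yes | eye | study eye | yes | no | 1 |
| 2 | yes | non-eye | study eye | yes | yes | **2** |
| 3 | no | eye | study eye | no | no | **0** |
| 4 | no | eye | non-study eye | no | yes | 1 |
| 5 | no | eye | no eye recorded | no | no | **0** |
| 6 | no | non-eye | study eye | no | yes | 1 |
| 7 | no | non-eye | non-study eye | no | yes | 1 |
| 8 | no | non-eye | no eye recorded | no | yes | 1 |

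Five of the eight rows behave. Row 2 is counted twice; rows 3 and 5 are not counted at all.

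**Effect on totals.** Let *a* be the number of TEAEs in row 2 and *b* the number in rows 3 and 5 together. Then

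ocular events + non-ocular/non-study-eye events = all TEAEs + *a* − *b*.

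The totals agree only if *a* = *b*, and agreement with *a* = *b* > 0 would hide both faults. This identity concerns events. Subject counts would not add up under any split, because one subject can have events of both kinds.

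**Which tables are touched.** SAP 7.1.2 lists six table types. The last is for ocular TEAEs only, so five can have a non-ocular/non-study-eye version: overall summary, SOC and preferred term, maximum severity, relationship, and serious events (if the event is serious). Row 2 events add entries to those versions and leave the ocular tables as they should be. Rows 3 and 5 remove entries from the split tables. Row 3 in particular would leave a study-eye event out of the ocular tables. The tables of all TEAEs are correct throughout.

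**Weight of one subject.** SAP 2.2 gives "A total of approximately 150 males and females" and the protocol's Treatment Phase text says "There are three treatment groups in the study and 1:1:1 randomization", so an arm has about 150/3 = 50 subjects. One subject is then 1/50 = 2.0 percentage points. For assumed arm sizes of 55 to 45 the range is 1/55 = 1.8 to 1/45 = 2.2. A row 2 event adds this to the overall non-ocular/non-study-eye rate only if it is the subject's sole entry there. This is the weight of any one subject in any table. It does not measure the defect, because the number of such subjects is not given.

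**After the change proposed below.** With the second class defined as everything not classed as ocular, all eight rows give exactly 1, and the event counts add up to all TEAEs.

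**The case against.** The strongest reply is that the lead sentence and the name of the second class already imply an exclusive split: an event classed as ocular for the study eye is neither non-ocular nor in the non-study eye. On that view the SOC clause is loose drafting that a programmer would read sensibly. As to intent, this is right. But the clause on non-eye SOCs is explicit and carries no exclusion, so following it as written gives the overlap. Reading the intent into it also does not place rows 3 and 5.

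A second reply is that the rule may be settled elsewhere. The table shells are a separate document, the eCRF is not among the documents, SAP section 11 is blacked out, and protocol 9.6.5.3 has blacked-out text too. This stands as a limit on what can be concluded. The visible redactions in SAP 7.1.2 do not fall within the classification sentences, however, and a shell that said otherwise would be overriding the SAP.

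A third reply is that little is at stake. The protocol says "No formal statistical testing will be conducted for the safety analyses", so no test or error rate changes, and the double count leaves the ocular tables complete. That stands for the double count. It does not cover row 3, which would drop a study-eye event from the ocular tables.

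A reader might go further and infer that the non-ocular rates will be inflated by about 2 points, or that the implant arms will be hit harder because protocol 9.6.5.2 expects more surgical complications there. The documents support neither. They give no coded terms and no event counts, so neither the frequency nor any imbalance between arms can be stated. It would also be wrong to assume that eye-SOC events with no eye recorded will be rare because the AE form must be filled in completely: the items listed in protocol section 10 do not include the eye affected.

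**Conclusion.** The definitions in SAP 7.1.2 do not deliver the two-way split that the section announces. Read literally, a study-eye event coded to a non-eye SOC is counted in both classes. An eye-SOC event not marked ocular for the study eye and not in the non-study eye is counted in neither. This is a stated rule that gives a wrong tabulation if followed, not merely a missing detail.

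The consequence is modest. The affected tables are descriptive and those of all TEAEs stay correct. The number of affected events cannot be determined from the documents and may be zero.

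The conclusion rests on two assumptions: that no unseen document supplies a precedence rule, and that the eCRF can hold the combinations in the table. Row 2 needs only a study-eye mark on an event coded outside the eye SOC. Row 3 needs a form on which location and the ocular mark are recorded separately; if they are one field, row 3 cannot arise.

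**What to change.** Replace the SOC-based clause in SAP 7.1.2 with a complement, for example: *Ocular TEAE: any TEAE indicated for the study eye on the eCRF AE form, whatever its SOC. Non-ocular/non-study-eye TEAE: every TEAE not classed as ocular.* Use SOC only as a row heading within each class.

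A complement sends doubtful events to the non-ocular class by default. Before database lock, therefore, query eye-SOC TEAEs that have no eye recorded, and those located in the study eye but not marked ocular. If the shells or the eCRF instructions already hold a precedence rule, bring the SAP wording into line with it. No separate rule for bilateral events is needed for this purpose.

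The cost is one phrase in the SAP, one derivation flag and a small data check.
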